Sample acquisition and processing: The default method for BAL specimen acquisition will be via the blind or “mini” BAL technique [18], using an 85 mm by 4 mm bronchial diagnostic catheter (Combicath, ® Prodimed, Neuilly-en-Thelle, France). The catheter is passed through the artificial airway until resistance is met. It is then withdrawn approximately 1 cm and the inner lavage catheter is deployed. Lavage is then performed with 20 – 40 mL of sterile saline.

The BAL will be obtained bronchoscopically if bronchoscopy is being performed for another indication (e.g., pulmonary toilet, percutaneous dilational tracheostomy). Lavage is performed using 20-40 mL of normal saline lavage into the lobar bronchus that appears most abnormal on CXR.

Using a 0.001 calibrated loop, vortexed BAL specimens will be plated onto sheep blood, MacConkey, and Chocolate agar at 35°C - 37°C in CO₂. Plates will be examined after 24, 48, and 72 hours prior to issuing a final negative report. 100 or more colonies per plate is considered significant and represents $\geq 10^5$ cfu/mL.

Statistical Analyses:

Power analysis: Power analysis was performed using SAS Version 9.1 (SAS, Inc., Carey, NC, *proc power*). The Analysis was based on a non-inferiority study design, defined as a difference in outcomes between the 4 day and 8 day groups of < 10%. Furthermore, as the intention was to show non-inferiority, tests were one-sided using an alpha error level of 0.10. The beta error level was set at 0.20 for 80% power. Analysis for the outcome of VAP recurrence returned the largest sample size. From 2010-2012, during which time VAP was treated with ≥ 8 days of therapy, the incidence of recurrent VAP in the DHMC surgical ICU was approximately 25%. Projecting a recurrence rate after 4 days of treatment of 35% returns a total sample size of 103..

Interim Analysis: An interim analysis will be conducted for all outcomes after 50% accrual (n_{total}=50).

Data Analysis: Data analyses will be performed using SAS Version 9.1 (SAS, Inc., Carey, NC). Data will be analyzed using an intention-to-treat strategy (i.e., patients randomized to receive 4 days of antibiotic therapy will be analyzed with this group even if they receive longer courses). Data will be expressed as median (range) or number (%). Normality of continuous variables will be assessed using the

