Kolmogorov-Smirnov test. Differences in the means of continuous variables that are distributed normally will be assessed using the Student's t-test. Differences in the medians of continuous variables that are not distributed normally will be assessed using the Wilcoxon Rank Test. Proportions of categorical variables will be compared using the chi-squared test. When expected cell counts are < 5, Fischer's exact test will be used. Univariate analysis of categorical outcomes will be expressed as the relative risk with 95% confidence intervals. A logistic regression model will be fit to address possible confounding by differences in baseline parameters between groups. Baseline variables associated with randomization status at the $p<0.25$ level by univariate analysis will be added to the model using a forward selection method. The overall contribution of the fitted model to predicting variability in the outcome of interest will be assessed using the likelihood ratio chi-squared test. The independent contribution of individual variables will be assessed using the Wald chi-squared test. Model fit was will be assessed using the Hosmer-Lemeshow goodness-of-fit chi-squared statistic, with $p>0.05$ indicating acceptable model calibration. The alpha error level is defined at 0.05, with statistical significance set at $p<0.05$.

Adverse Event Monitoring and Reporting: Adverse event monitoring will occur daily. The safety of the study will be monitored by an independent, external Data Safety Monitoring Board, consisting of a medical intensivist, and an infectious disease physician. The committee will meet biannually and submit written reports to the IRB.

References:

1. Edwards, J.R., K.D. Peterson, Y. Mu, S. Banerjee, K. Allen-Bridson, G. Morrell, et al., National Healthcare Safety Network (NHSN) report: data summary for 2006 through 2008, issued December 2009. *Am J Infect Control* 2009;37:783-805
2. Neu, H.C., The crisis in antibiotic resistance. *Science* 1992;257:1064-73
3. Mahgoub, S., J. Ahmed, and A.E. Glatt, Completely resistant *Acinetobacter baumannii* strains. *Infect Control Hosp Epidemiol* 2002;23:477-9
4. Kollef, M.H. and V.J. Fraser, Antibiotic resistance in the intensive care unit. *Ann Intern Med* 2001;134:298-314
5. Bradley, J.S., R. Guidos, S. Baragona, J.G. Bartlett, E. Rubinstein, G.G. Zhanel, et al., Anti-infective research and development--problems, challenges, and solutions. *Lancet Infect Dis* 2007;7:68-78

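### No planned estimate is on the scale of the 10-point non-inferiority criterion: the crude result is a relative risk and the adjusted one comes from a logistic model

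*Combined protocol and SAP*

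**What the plan says.** Three statements in the combined protocol and SAP, under Statistical Analyses, bear on the scale of the treatment effect.

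- **Criterion (Power analysis).** Non-inferiority is "defined as a difference in outcomes between the 4 day and 8 day groups of < 10" percent. For the 8-day arm, "the incidence of recurrent VAP in the DHMC surgical ICU was approximately 25" percent, and for the 4-day arm, "Projecting a recurrence rate after 4 days of treatment of 35% returns a total sample size of 103".
- **Crude result (Data Analysis).** "Univariate analysis of categorical outcomes will be expressed as the relative risk with 95% confidence intervals".
- **Adjusted result (Data Analysis).** "A logistic regression model will be fit to address possible confounding by differences in baseline parameters between groups". Baseline variables associated with study arm at p<0.25 "will be added to the model using a forward selection method". Likelihood-ratio, Wald and Hosmer-Lemeshow statistics are specified for the model, but no measure of the adjusted treatment effect is.

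Neither paragraph plans a risk difference, crude or adjusted, or says how any result will be compared with the 10% criterion.

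**The concern.** The criterion is on the difference scale, the crude result on the relative-risk scale, and the adjusted result comes from a model whose usual output is an odds ratio. Nothing links the three. Two things are at stake.

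1. **The decision.** A ratio corresponds to a number of percentage points only once the control risk is known. Followed as written, the plan produces no estimate that answers whether 4 days is within 10 points of 8 days.
2. **The comparison of crude with adjusted.** The model is there to deal with confounding, so a reader will naturally set its result beside the crude one. With a common outcome those two numbers differ even when nothing is confounded.

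**Working it through.** **Inputs.** From the Power analysis paragraph: 25% recurrence with 8 days, 35% with 4 days, total 103. Assumed: 1:1 allocation (the ratio is not stated) and the strength of the prognostic covariate, shown as a range. Whether 103 follows from the stated design inputs is a separate question; it is used here only to count events.

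**Step 1: one effect on three scales.**

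- Risk difference: 0.35 − 0.25 = 0.10, which matches the plan's 10% and is why the criterion is read as percentage points.
- Relative risk: 0.35/0.25 = 1.40.
- Odds ratio: (0.35/0.65)/(0.25/0.75) = 1.615.

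**Step 2: ratios do not fix a difference.** For control risk p, a relative risk of 1.40 gives a difference of p × 0.40. An odds ratio of 1.615 gives a 4-day risk of o/(1+o), with o = 1.615 × p/(1−p).

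| Control risk | Difference at RR 1.40 | Difference at OR 1.615 |
|---|---|---|
| 5% | 2.0 points | 2.8 points |
| 10% | 4.0 points | 5.2 points |
| 25% | 10.0 points | 10.0 points |
| 40% | 16.0 points | 11.9 points |

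Both ratios match the criterion only at the planned 25%.

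**Step 3: adjustment without confounding.** Take a binary covariate with 50% prevalence in each arm and odds ratio k for recurrence. Hold the overall risks at 25% and 35% by solving, for each arm t,

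0.5 × expit(a_t) + 0.5 × expit(a_t + ln k) = risk in arm t,

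where expit(u) = 1/(1 + e^(−u)). The adjusted odds ratio is then exp(a_4 − a_8), the subscripts being days of treatment.

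| k (assumed) | Adjusted odds ratio |
|---|---|
| 2 | 1.635 |
| 6 | 1.744 |
| 10 | 1.824 |

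Check at k = 6. The stratum risks are 10.0% and 40.0% with 8 days (mean 25%), and 16.23% and 53.77% with 4 days (mean 35%). The stratum odds ratios are (0.1623/0.8377)/(0.10/0.90) and (0.5377/0.4623)/(0.40/0.60), both about 1.744. The stratum differences are 6.23 and 13.77 points, mean 10.0. The odds ratio has moved from 1.615; the averaged risk difference has not.

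For a normally distributed covariate, the adjusted odds ratio is 1.655, 1.766, 1.934 and 2.152 at log-odds standard deviations of 0.5, 1, 1.5 and 2. At equal risks (25% in both arms) the relative risk, crude odds ratio and adjusted odds ratio are all 1.

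**Step 4: what makes up the gap.** On the log scale, moving from RR 1.40 to OR 1.615 accounts for ln(1.615/1.40) = 0.143. The whole gap to the adjusted odds ratio is ln(1.635/1.40) = 0.155 at k = 2 and ln(1.824/1.40) = 0.265 at k = 10. So 92% to 54% of it is the plain switch of measure, which needs no assumption about covariates.

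**Step 5: single trials of 103 patients.** In about 2,000 simulated trials per scenario at 25% versus 35%, with a normal covariate (log-odds standard deviation 1) and no confounding, the median crude relative risk was 1.39 and the median adjusted odds ratio 1.79. The mean crude risk difference was 9.7 points and the mean difference standardised from the same logistic fits was 9.8, against a true 10.0. The adjusted odds ratio lay further from 1 than the crude relative risk in 89% of these trials, and in 96% when the covariate had no effect.

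**Step 6: events available.** 51.5 × 0.25 + 51.5 × 0.35 = 30.9, or about 31 recurrences.

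**The case against.** Several points against this are fair.

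- **The odds ratio is inferred.** A reader might conclude that the plan commits to an adjusted odds ratio. It does not: it names a model and some tests. The same model can yield a risk difference, so the model is not at fault. What stands is that no measure is named and none is linked to the criterion.
- **The adjusted result need not look larger.** A reader might infer that it always will. That needs a true difference and a prognostic covariate, and it is not certain in any one trial. The trial's hypothesis is equal effectiveness, under which every ratio has a true value of 1.
- **The balanced covariate is a device.** Under the p<0.25 rule a perfectly balanced covariate would not enter the model. Step 3 isolates the mechanism and does not imitate the planned analysis. Prognostic covariates that do enter bring the same mechanism with them, mixed with whatever chance imbalance admitted them.
- **The covariate shift is small beside sampling error.** With 51.5 per arm the standard error of the crude log odds ratio is √[1/12.875 + 1/38.625 + 1/18.025 + 1/33.475] = 0.435, giving a 95% interval of about 0.69 to 3.79. The move from 1.615 to 1.744 is 0.077 on the log scale, about 0.18 of a standard error.
- **Misreading is not prescribed.** The plan has no rule that judges confounding by the change from crude to adjusted. The risk lies in how the two figures would naturally be read side by side.
- **The criterion's scale is also inferred.** The words absolute or risk difference do not appear. But a relative 10% would put the limit at 1.10 × 25% = 27.5%, which does not fit the projected 35%.

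The crude relative risk is just as unlinked to the criterion as the logistic model. This widens the point beyond the adjusted analysis.

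**Conclusion.** The point holds as a mismatch of scales across the whole analysis. The criterion is a 10-point difference, and neither planned estimate can be set against it without a further step that the plan does not describe. At the planned rates the same effect reads as 10 points, 1.40 or 1.62, and as about 1.63 to 1.82 after adjustment for an assumed 50% binary covariate with odds ratio 2 to 10.

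In that range most of the distance between crude relative risk and adjusted odds ratio is the change from risks to odds, and the rest is non-collapsibility; none of it is confounding. With stronger covariates, such as the normal one with log-odds standard deviation 1.5 or 2, the second part becomes the larger.

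The documents do not support the stronger readings that an odds ratio is promised, that adjustment must exaggerate the effect, or that logistic regression is the wrong model. The conclusion rests on reading the criterion as percentage points and on the planned 25% and 35%; the size of the adjustment shift also rests on the assumed covariate. It bears on how the non-inferiority result is read. It does not invalidate the trial, and the analysis should be changed because a better one is cheap.

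**What to change.** In the Data Analysis paragraph:

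1. Report the crude risk difference (4 days minus 8 days) with a confidence interval, and read it against the 10-point criterion. Keep the relative risk beside it. State the confidence level, since the Power analysis says "tests were one-sided using an alpha error level of 0.10" while Data Analysis uses 0.05 and 95% intervals.
2. Name a few prognostic baseline covariates in advance, replacing selection by imbalance at p<0.25 and forward steps. Fit the logistic model with these and study arm.
3. From that model, predict each patient's risk under 4 days and under 8 days, average each over all patients, and report the adjusted risk difference and relative risk with delta-method or bootstrap intervals.
4. Give the odds ratio only as supplementary output, with a note that it is not comparable with the relative risk.

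The second item is a condition of the third. If covariates were still chosen from the data, delta-method intervals would ignore the selection, a bootstrap would have to repeat it, and the choice of covariates could affect the non-inferiority conclusion.

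The cost is a little extra analysis work and having to choose the covariates beforehand; with about 31 expected events there is room for only a few. No extra data or patients are needed.

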Study Flow & Stop Criteria: The trial will be reported in accordance with the recommendations of the CONSORT Statement [28]. IRB approval will be obtained. All subjects or their legally authorized representative will provide written consent for study participation. The trial is registered with the US National Institutes of Health (ClinicalTrials.gov Identifier NCT01994980).

Screening will occur daily by study personnel. Eligible patients will be approached as soon as possible after inclusion criteria are met (i.e., 1-3 days prior to randomization). Randomization will occur using a computer-generated block pattern on the morning following the fourth day of appropriate antibiotic therapy.

Empiric antibiotic therapy will be instituted as soon as possible following BAL acquisition. The default antibiotic will be ceftriaxone 2 gram IV q24 hours. Patients with potential allergies to cephalosporins will receive levofloxacin 750 mg IV q24hours. Pre-existing treatment for a non-

pulmonary infection with at least one antibiotic that has appropriate activity against the VAP pathogen may be substituted for the default antibiotic. Once sensitivity data become available (approximately 72 hours after BAL acquisition), therapy may be de-escalated to a more narrow-spectrum agent (e.g., cefazolin) as indicated.

The default duration of antibiotic therapy will be determined by study group assignment; the treatment team will be asked to adhere to study group assignment whenever possible. However, the treatment team may choose to extend the duration of antibiotic therapy based on clinical circumstances, such as deterioration in hemodynamic or respiratory status that is believed to be related to incompletely treated VAP, or continued treatment of a non-pulmonary infection. The treatment team may also decide to extend the duration of antibiotic therapy based on the results of serial procalcitonin measurements. Finally, the treatment team may decide to extend the duration of antibiotic therapy based on the results of the BAL obtained the day after completion of therapy. These clinical decisions will take precedence over study group assignment.

Patients will be followed for 28 days or until hospital discharge, whichever occurs first. Please see attached data collection tool for detailed information.

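### Covariates for the adjusted logistic model are chosen by chance imbalance between randomised groups, with no stated forward-entry level; a short list named in advance would be reproducible and, if mostly prognostic, more precise.

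*Combined protocol and SAP*

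**What the plan says.** Under Statistical Analyses, Data Analysis, the purpose of the model is stated: "A logistic regression model will be fit to address possible confounding by differences in baseline parameters between groups". The selection rule follows: "Baseline variables associated with randomization status at the" p<0.25 "level by univariate analysis will be added to the model using a forward selection method". No covariate is named in advance, the binary outcome to be modelled is not identified, and the forward step has no entry level of its own. The only other level in that paragraph is general: "The alpha error level is defined at 0.05".

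The unadjusted analysis is also planned: "Univariate analysis of categorical outcomes will be expressed as the relative risk with 95% confidence intervals". Nothing says which of the two decides the trial. Under Study Flow & Stop Criteria, "Randomization will occur using a computer-generated block pattern". Baseline Variables lists 12 candidates. The Power analysis sets a 10-point non-inferiority margin, and "tests were one-sided using an alpha error level of 0.10".

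**The concern.** After randomisation, an association between a baseline variable and group is chance. A screen on that association does not ask whether the variable predicts outcome, and outcome prediction is what makes adjustment useful. A strong predictor that happens to be balanced is left out, while an irrelevant variable that happens to be imbalanced can go in.

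The forward step can be read in three ways:

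- p<0.25 on imbalance is itself the entry rule, so every screened variable enters.
- Entry is an outcome test at 0.05.
- Entry is an outcome test at another level, such as 0.25.

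Two analysts following the same sentence could therefore report different adjusted results. At stake are the precision of the adjusted comparison and whether it can be regarded as specified in advance.

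**Working it through.** **Plan's own figure.** The plan gives none for the precision of the adjusted model. N=103 and the 25% and 35% recurrence rates are taken as stated in the Power analysis; how 103 was derived is a separate question.

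**Screen.**

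- Expected number passing: 12 × 0.25 = 3.0. If prior and current antibiotics are counted apart and baseline CPIS and procalcitonin are added, 15 × 0.25 = 3.75.
- Chance that at least one passes: 1 − 0.75^12 = 0.97.
- Chance that neither of two independent prognostic variables passes: 0.75² = 0.56.
- Share of chance-imbalance variance held by the variables that pass: with c = 1.150, 1 − (0.75 − 2cφ(c)) = 0.724.
- Expected recurrences, assuming equal arms: 51.5 × 0.25 + 51.5 × 0.35 = 30.9, about 10 per covariate for a list of three.

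**Simulation assumptions (not in the documents).** Permuted blocks of 4; 12 independent normal candidates, two of them prognostic with equal log-odds slopes per SD; marginal risks fixed at 25% and 35%; 12,000 trials per slope. The risk difference is standardised over the fitted logistic model. Slopes of 0.3/0.5/0.7/1.0 correspond to a joint AUC of 0.62/0.68/0.74/0.81.

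| SD of risk difference | 0.3 | 0.5 | 0.7 | 1.0 |
|---|---|---|---|---|
| Unadjusted | 0.0909 | 0.0897 | 0.0898 | 0.0905 |
| Fixed three, two prognostic | 0.0906 | 0.0874 | 0.0840 | 0.0800 |
| Fixed three, one prognostic | 0.0916 | 0.0895 | 0.0877 | 0.0866 |
| Plan, all screened enter | 0.0930 | 0.0913 | 0.0886 | 0.0869 |
| Plan, entry 0.25 | 0.0924 | 0.0904 | 0.0879 | 0.0857 |
| Plan, entry 0.05 | 0.0915 | 0.0895 | 0.0871 | 0.0843 |

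The bootstrap SE of the percentage changes is 0.2–0.5 points.

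**List with two of three prognostic.** The plan's SD is larger by 2.7/4.5/5.5/8.6% if all screened variables enter and by 1.0/2.4/3.7/5.3% at entry 0.05. With 15 candidates, six of them binary, the excess is 1.5–5.0% at slope 0.3 and 5.9–9.9% at 1.0.

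Share of the available precision gain that the plan gives up:

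- Slope 1.0: the fixed list changes the SD by −11.5% against unadjusted and the plan by −4.0 to −6.8%. (11.5 − 6.8)/11.5 = 41%; (11.5 − 4.0)/11.5 = 65%.
- Slope 0.7: −6.5% against −1.3 to −3.0%. (6.5 − 3.0)/6.5 = 54%; (6.5 − 1.3)/6.5 = 80%.
- Slope 0.5: the fixed list gains 2.5%. Entry 0.05 gains 0.2% (0.0895/0.0897), and all-enter loses 1.8% (0.0913/0.0897).
- Slope 0.3: the fixed list gains 0.3%, while the plan is 0.7–2.4% worse than unadjusted.

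**List with one of three prognostic.** Against entry 0.05 the ratios are 0.0916/0.0915, 0.0895/0.0895, 0.0877/0.0871 and 0.0866/0.0843: level at the two lower slopes, then 0.7% and 2.7% worse.

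**Error and power.** At equal 25% risks, the two-sided 0.05 Wald test rejects in 0.040–0.056 of trials under the plan and 0.047–0.053 with the fixed list. At 25% against 35%, its power is 0.20/0.21/0.23/0.25 with the fixed list (two prognostic) and 0.19–0.20 under the plan. With equal 25% risks and a one-sided 90% bound against the 10-point margin, non-inferiority is reached in 46/50/53% (fixed) and 45–46/46–47/47–48% (plan) at slopes 0.3/0.7/1.0.

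**Ambiguity.** The all-enter and 0.05-entry readings differ by a median of 1.2–1.4 points of risk difference, and by more than 2 points in 30–36% of trials. In a second simulation, with three prognostic variables at odds ratios of 1.5 or 2 per SD, entry at 0.05 and at 0.25 gave different models in 46–51% of trials at 25% against 35%.

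**The case against.** The model is offered as a check on baseline imbalance beside a valid unadjusted relative risk, not as a device for precision. The screen partly serves that purpose, since the variables that pass hold about 72% of the chance-imbalance variance. If forward entry tests the outcome, it does select on prognosis within the screened pool. The standardised risk difference and the one-sided 90% bound are yardsticks brought in here; the Data Analysis section plans neither for this model. The largest ambiguity figures use the all-enter reading, which leaves the forward step nothing to select. A 1.2–1.4 point shift is also small beside an SD of about 9 points, and entry at 0.05 and at 0.25 give nearly the same precision.

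All of this stands, and it limits the size of the point. It does not justify choosing covariates by chance imbalance or leaving the entry level open.

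A reader might infer that the planned rule is always less precise than a fixed list. The figures do not support that: a list with one prognostic variable in three does no better than the plan at entry 0.05, and the documents do not show which variables predict recurrence. A reader might also infer that the rule invalidates the trial's conclusion. The documents do not support that either, because they retain the unadjusted comparison and do not make the logistic model decisive, and no material inflation of type I error was found.

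**Conclusion.** The point holds as a minor weakness of efficiency and pre-specification. The covariate pool is set by chance, and the entry level is open to several readings.

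With a mostly prognostic list, the plan's risk-difference SD is about 1–9% larger. The plan then gives up about 41–65% of the available gain at slope 1.0, 54–80% at 0.7, and nearly all or more of it at 0.5 and below. With a weak list there is no gain in precision, and what remains is a reproducible model fixed in advance.

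These sizes rest on assumed covariate effects, independent candidates and 1:1 allocation, and they apply on the risk-difference scale. The conditional log odds ratio has a larger SD under the fixed list (0.488–0.574 against 0.450–0.455 unadjusted) because it is a different estimand; the power of its Wald test is not lower.

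**What to change.** Delete the p<0.25 screen and the forward selection. Before the interim analysis at n=50, name VAP recurrence, the outcome that sets the sample size, as the outcome of the adjusted model. At the same time, name about three baseline variables already collected and judged prognostic for recurrence on clinical grounds, for example admission APACHE II, age and comorbidity index. Include them whatever their imbalance, but do not force all three into models for outcomes with few events. Keep the unadjusted comparison. Report the adjusted result as a standardised risk difference with a confidence bound, so that it lies on the scale of the 10-point margin.

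The cost is about two sentences in the analysis section and no new data. The choice rests on clinical judgement: a weak list gains nothing, costs about 1–2% in SD against unadjusted, and can be slightly less precise than the present rule.

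### The trial is sized to show non-inferiority within 10 points, but no planned analysis tests that margin, and the two stated alpha levels are not reconciled

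*Combined protocol and SAP*

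**What the plan says.** The hypothesis at the end of the Background has two parts: that four days of therapy is as effective as eight, and that it reduces antibiotic exposure. The Outcomes section makes effectiveness and antibiotic exposure the two main outcomes, and measures effectiveness by clinical, microbiologic and biomarker response.

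Under Statistical Analyses, Power analysis, the design is non-inferiority, "defined as a difference in outcomes between the 4 day and 8 day groups of < 10" percent, and "tests were one-sided using an alpha error level of 0.10", with 80% power. "Analysis for the outcome of VAP recurrence returned the largest sample size", and "Projecting a recurrence rate after 4 days of treatment of 35% returns a total sample size of 103", against about 25% historically with eight or more days. Recurrence itself is listed under Additional Outcomes.

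Under Data Analysis, "Data will be analyzed using an intention-to-treat strategy". For categorical outcomes, "Proportions of categorical variables will be compared using the chi-squared test" (Fisher's exact test for small expected counts), and "Univariate analysis of categorical outcomes will be expressed as the relative risk with 95% confidence intervals". Logistic regression adjusts for baseline imbalance. The section closes: "The alpha error level is defined at 0.05, with statistical significance set at" p<0.05. It mentions neither non-inferiority, nor the 10% margin, nor a risk difference, nor a confidence limit to be compared with a margin.

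**The concern.** Every test in the Data Analysis section has a null hypothesis of no difference. A non-inferiority claim needs the opposite null, that the shorter course is worse by at least the margin, and nothing planned addresses it. The margin and its alpha appear only where the sample size is justified.

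The two alpha levels, one-sided 0.10 for sizing and 0.05 of unstated sidedness for analysis, are not reconciled. The 0.05 may be meant only for superiority questions such as antibiotic exposure, but the documents do not say so.

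The coverage of the margin is also unclear. The Power analysis speaks of outcomes in general without listing them, and a percentage margin does not fit the 0-10 clinical score.

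At stake is half of the trial's hypothesis. The decision rule, the alpha and the outcome for the effectiveness claim could all be settled after the data are seen.

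**Working it through.** **Inputs.** From Power analysis: 8-day recurrence 25%, projected 4-day recurrence 35%, margin 10% (read as absolute points, because the example is 25% against 35%), one-sided alpha 0.10, power 80%, total N 103. From Data Analysis: chi-squared test, 95% relative-risk interval, alpha 0.05. Assumed: 1:1 allocation, with 51 patients in the 8-day arm and 52 in the 4-day arm.

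**The plan's own figure.** For a margin test on the risk difference, n per arm = [p8(1−p8) + p4(1−p4)] × (z_alpha + z_beta)² / [0.10 − (p4 − p8)]².
- At 25% and 35% the denominator is (0.10 − 0.10)² = 0, so no finite N exists.
- At 25% in both arms: 0.375 × (1.2816 + 0.8416)² / 0.01 = 169.05, so 170 per arm and 340 in total.

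The stated 103 is therefore not the size of a two-arm test of a 10-point margin on the stated inputs. It cannot show that such a test was intended for the analysis.

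**What the planned tests would show.** Exact enumeration over Binomial(51, p8) × Binomial(52, p4). The margin column is the probability that the upper one-sided 90% Wald bound on p4 − p8 lies below 0.10.

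| True p8, p4 | Chi-squared p>0.05 | 95% RR interval includes 1 | Margin met, one-sided 0.10 |
|---|---|---|---|
| 25%, 35% | 0.803 | 0.824 | 0.101 |
| 25%, 40% | 0.625 | 0.662 | 0.035 |
| 15%, 25% | 0.762 | not needed | 0.106 |
| 35%, 45% | 0.824 | not needed | 0.111 |

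The middle columns would be false-acceptance rates only if non-significance were read as equal effectiveness. The plan states no such rule, so they illustrate the gap and are not the plan's error rate.

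**Does alpha change the verdict?** Fix 13/51 (25.5%) in the 8-day arm. The bound is d + z × sqrt[p8(1−p8)/51 + p4(1−p4)/52]. For 12/52, d = 0.231 − 0.255 = −0.024 and the standard error is 0.0845, so at one-sided 0.10 the bound is −0.024 + 1.2816 × 0.0845 = 0.084.

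| 4-day count | One-sided 0.10 | 0.05 | 0.025 |
|---|---|---|---|
| 10/52 | 0.042 | 0.072 | 0.098 |
| 11/52 | 0.063 | 0.094 | 0.120 |
| 12/52 | 0.084 | 0.115 | 0.141 |
| 13/52 | 0.105 | 0.136 | 0.163 |

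So 12/52 passes at 0.10 and fails at 0.05. If the 0.05 is two-sided (one-sided 0.025), 11/52 also changes verdict. From 13/52 to 22/52 (25.0% to 42.3%) the uncorrected chi-squared test is non-significant (p = 0.95 to 0.07) while the margin is missed at all three levels. At 22/52 the relative risk is 1.66 (0.94 to 2.92) and the one-sided 0.10 bound is 28.6 points.

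**Can the relative-risk interval stand in?** Ten points equals a relative risk of 0.25/0.15 = 1.67, 0.35/0.25 = 1.40 or 0.45/0.35 = 1.29 at 8-day rates of 15%, 25% or 35%. Without a stated margin on that scale, the interval does not test the criterion.

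**Power of the margin test at 103 patients, equal true rates.**

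| Both arms | One-sided 0.10 | 0.05 | 0.025 |
|---|---|---|---|
| 15% | 0.558 | 0.422 | 0.317 |
| 25% | 0.458 | 0.332 | 0.223 |
| 35% | 0.431 | 0.283 | 0.191 |

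At the plan's own projection (25% and 35%) the chance of concluding non-inferiority is about 10%, 5% or 2.7%.

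**The case against.** The Power analysis sits under the same Statistical Analyses heading and states design, margin, sidedness and alpha. A sympathetic reader could take it as the non-inferiority criterion, with the 0.05 as the default for everything else. It also refers to outcomes in the plural, so recurrence is evidently one of those covered. That much stands: a criterion exists, and the two alphas are an ambiguity, not a proven contradiction. But the Data Analysis section sets its own methods and alpha without exempting any outcome. Even on the generous reading, no estimator or decision rule applies the margin.

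It can also be said that the 80% figure describes a misreading the plan never endorses, and that the alpha effect is modest. Both are fair. With 13/51, one count changes verdict between 0.10 and 0.05, and at 25% in both arms the two levels disagree in about 13% of trials (0.458 − 0.332). The missing margin test depends on neither figure.

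**Conclusion.** The concern holds. Following the plan exactly yields no test of the effectiveness hypothesis against the plan's own margin, so this is the wrong analysis for the stated aim and not merely missing detail. At 103 patients a real 10-point excess in recurrence would leave the planned chi-squared test non-significant about 76% to 82% of the time for 8-day rates of 15% to 35%, against 10% to 11% acceptance by a one-sided 0.10 bound on the risk difference. These sizes rest on 1:1 allocation, a margin in absolute points and the Wald bound. Exchanging the arm sizes barely moves them: at 25% and 35%, 0.797 non-significant and 0.103 accepted.

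**What to change.** Amend the Data Analysis section before the data are analysed:

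1. List the outcomes for which non-inferiority will be claimed. For recurrence and any other adverse binary outcome, report the intention-to-treat risk difference (4-day minus 8-day) with an upper confidence bound, and declare non-inferiority only if the bound is below +10 points. For microbiologic and biomarker response, where higher is better, compare the lower bound with −10 points. Name the interval method. Make no such claim on the clinical score unless a margin in score points is stated.
2. State that p>0.05 on a difference test, or a relative-risk interval containing 1, is not evidence of non-inferiority.
3. State alpha and sidedness by outcome: one level for the non-inferiority test, identical in the power and analysis sections, and 0.05 for superiority tests such as antibiotic exposure.
4. Restate the power of the margin test at 103 patients, both for equal true rates and for the projected 25% and 35%.

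Because the treatment team may extend therapy in either group, which can draw the groups together, a supporting per-protocol analysis beside intention-to-treat would be sensible.

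The cost is wording and a little extra analysis of data already collected. The price is candour about power: about 46%, 33% or 22% at one-sided 0.10, 0.05 or 0.025 with both rates at 25%. Reaching 80% would need 340, 464 or 590 patients. The amendment exposes that shortfall; it does not create it.
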